9.2.2 Appropriateness of Measurements

The primary efficacy endpoint in this study is the PFS rate, defined as the proportion of patients alive and progression-free at Week 12. Patients will be progression-free if they have no evidence of progressive disease (per RECIST version 1.1) from the start of treatment to Week 12. The RECIST guidelines recognize that the proportion progression-free at a pre-specified time point is an appropriate to assess the anti-tumor activity of agents such as antroquinonol, where biological activity is more likely to translate into stabilization of disease.²⁵

Tumor response, based on radiological measurement, is a standard and well accepted efficacy endpoint in clinical development. Response to study drug will be assessed in this study using RECIST version 1.1 (see [Appendix 1](#)), an internationally standardized and widely accepted standard for measuring response to treatment in cancer.²⁵

The secondary efficacy measures of objective response rate (ORR), disease control rate (DCR), duration of overall tumor response (DR), PFS, overall survival (OS) and time to progression (TTP) are also well accepted efficacy endpoints in clinical development for oncology studies and in line with recommendations in the European Medicine's Agency (EMA), Committee for Medicinal Products for Human Use (CHMP) Guideline on the Evaluation of Anticancer Medicinal Products in Man (EMA/CPMP/205/95/Rev.4, 2012)²⁶; and the United States (US) Food and Drug Administration (FDA) Guidance for Industry on Clinical Trial Endpoints for the Approval of Cancer Drugs and Biologics (US Department of Health and Human Services, May 2007).²⁷

The safety and PK endpoints in this study are standard and well understood endpoints in clinical oncology. The corrected QT (QTc) assessment strategy for this study is based on recommendations in the International Conference on Harmonisation (ICH) E14 guideline²⁸ and is designed to focus on the collection of cardiac safety information. There are no concerns for cardiotoxicity based on the mechanism of action, the nonclinical toxicology studies, or the limited clinical information available to date. Twelve-lead ECGs are required during Screening, during treatment, and at the End of Treatment Visit, and as clinically indicated.

Quality of life will be assessed using EORTC QLQ C30 (QLQ-C30) and the Module on Lung Cancer (QLQ-LC13), which is a validated instrument for assessing quality of life (QoL) in patients with lung cancer.

The EORTC QLQ-C30 / EORTC QLQ-LC13 is comprised of a global health status scale, five functional scales (physical, role, emotional, cognitive, and social), three symptom scales (fatigue, nausea and vomiting, and pain), and several single items, as well as a module designed specifically for lung cancer. These QoL assessment tools are included in this study in order to evaluate the side effects of antroquinonol as well as the impact of treatment on patients' disease-related symptoms.

9.2.3 Risk/Benefit and Ethical Assessment

As known to the sponsor, no fatal or severe/serious adverse drug reaction has been reported by the marketed product (food supplement) of *Antrodia camphorata*.

Patients anticipated to be enrolled into the study will be non-squamous NSCLC patients with confirmed disease progression following two prior lines of systemic anti-cancer therapy for recurrent/metastatic disease (one of which should be a platinum-based **regimen**). As the dose utilized for this study is considered conservative and acceptable, and the patients targeted are mainly patients with rather limited treatment options, the risk and benefit assessment is deemed justifiable.

9.2.4 Early Termination

This study may be terminated at the discretion of the sponsor or any regulatory agency. A principal investigator (PI) may elect to discontinue or stop the study at his or her site for any reason including safety or low enrollment.

9.3 Selection of Study Population

9.3.1 Inclusion Criteria

Patients eligible for enrollment in the study must meet all of the following criteria:

1. Cytologically or histologically confirmed non-squamous NSCLC Stage IV (including pleural effusion)
2. Radiologically confirmed disease progression following greater than or equal to two, but less than or equal to four, prior lines of systemic anti-cancer therapy, one of which should be a platinum-based regimen, OR the patient has refused treatment with approved treatment modalities, OR the investigator feels that the patient is not a candidate for other systemic therapy. Patients with epidermal growth factor receptor (EGFR)-positive mutations should have been offered treatment with an EGFR-TK inhibitor prior to enrolment in this study. Adjuvant therapy with or without maintenance therapy would count as one line of systemic therapy. A line of therapy requires at least two 3-4 week complete cycles unless it was stopped due to toxicity, in which case it would count as one line of therapy
3. At least one radiologically measurable target lesion per RECIST version 1.1
4. Fresh or archival biopsy tissue available to determine KRAS tumor mutation status
5. At least 18 years of age at the time of signing informed consent
6. Life expectancy of at least 3 months
7. Written informed consent that is consistent with ICH Tripartite Guideline on Good Clinical Practice (GCP) guidelines
8. Patient or legally acceptable representative has granted written informed consent before any study-specific procedures (including special Screening tests) are performed
9. Eastern Cooperative Oncology Group (ECOG) performance score of 0, 1 or 2

10. Hemoglobin ≥ 9.0 g/dL; platelets $\geq 100 \times 10^9/L$; ANC $\geq 1.5 \times 10^9/L$ without the use of hematopoietic growth factors
11. Bilirubin and creatinine less than $2 \times$ upper limit of normal (ULN) for the institution
12. Albumin ≥ 2.5 g/dL
13. Aspartate aminotransferase (AST) and alanine aminotransferase (ALT) less than $5 \times$ ULN for the institution
14. Prothrombin time less than $1.5 \times$ ULN for the institution
15. Potassium, magnesium and phosphorus within the normal range for the institution (supplementation is permissible)
16. Willing to use two medically accepted and effective methods of contraception from the list below during the study (both men and women as appropriate) and for 3 months after the last dose of study drug:
 - Established use of oral, injected or implanted hormonal methods of contraception.
 - Placement of an intrauterine device or intrauterine system.
 - Barrier methods of contraception: Condom or Occlusive cap (diaphragm or cervical/vault caps) with spermicidal foam/gel/film/cream/suppository.
 - Male sterilization (with the appropriate post-vasectomy documentation of the absence of sperm in the ejaculate).
 - True abstinence: When this is in line with the preferred and usual lifestyle of the patient.
17. Recovery to \leq Grade 1 or baseline of any toxicities due to prior treatments, excluding alopecia

9.3.2 Exclusion Criteria

Patients meeting any of the following criteria must not be enrolled in the study:

1. Chemo-, hormone- or immunotherapy, within 4 weeks or within less than four half-lives of the date of first administration of study drug and/or persistence of toxicities of prior anti-cancer therapies which are deemed to be clinically relevant
2. Radiotherapy within the past 2 weeks prior to the date of first administration of study drug.
3. Previous treatment with a histone deacetylase (HDAC) inhibitor or an EGFR inhibitor within at least 4 weeks of the date of first administration of study drug
4. Treatment with any drug(s) known to be a strong inhibitor or inducer of CYP2C19, CYP3A4, CYP2C8, and CYP2E1, within 14 days of the date of first administration of study drug

5. Brain metastases which are symptomatic; patients with treated brain metastases are eligible with stable brain disease for at least 4 weeks without the requirement for steroids or anti-epileptic therapy
6. Inability to swallow oral medications or a recent acute gastrointestinal disorder with diarrhea e.g., Crohn's disease, malabsorption, or Common Terminology Criteria for Adverse Events (CTCAE) Grade > 2 diarrhea of any etiology at baseline
7. Other malignancies diagnosed within the past 5 years (other than curatively treated cervical cancer *in situ*, non-melanoma skin cancer, superficial bladder tumors Ta [non-invasive tumor] and TIS [carcinoma *in situ*], or non-metastatic prostate cancer stage 1 to 2, which has been previously treated with surgery or radiation therapy, and serum prostate-specific antigen is within normal limits [test performed within the past 12 months prior to the date of first administration of study drug])
8. Patients with any serious active infection (i.e., requiring an intravenous antibiotic, antifungal, or antiviral agent)
9. Patients with known HIV, active hepatitis B or active hepatitis C
10. Patients who have any other life-threatening illness or organ system dysfunction, which in the opinion of the investigator, would either compromise patient safety or interfere with the evaluation of the safety of the study drug
11. Known or suspected substance abuse or alcohol abuse
12. Women of child-bearing potential or men who are able to father a child unwilling to use two medically accepted and effective methods of contraception during the study (as specified in the inclusion criteria)
13. Pregnancy or breast feeding
14. Patient unable to comply with the protocol
15. History of clinically significant or uncontrolled cardiac disease, including congestive heart failure, angina, myocardial infarction, arrhythmia, including New York Heart Association functional classification of 3

9.3.3 Removal of Patients from Study or from Study Treatment

Patients may withdraw their consent to participate in the study and investigators may withdraw patients at any time without prejudice. Patients will be withdrawn from the study or study treatment if any of the conditions set below has occurred:

1. Documented disease progression according to the response criteria
2. Unacceptable toxicity
3. Patient decides to withdraw his/her informed consent
4. Investigator considers that the patient is no longer physically and/or psychologically able to remain in the study

5. Patient has developed a condition that requires treatment with a medication prohibited by the protocol
6. Patient develops adverse effects that the investigator considers a permanent cessation of the study drug is necessary
7. Non-compliance with study drug, protocol requirements, or study-related procedures
8. Patient's treatment is interrupted for more than 1 week and the investigator and Medical Monitor considers a permanent cessation of the study drug is necessary

The investigators should complete the evaluation items for the EOS Visit upon a patient's withdrawal. Tumor assessment does not need to be performed at the EOS Visit if this was conducted at the Day 84 Visit. For patients participating in the Extension Phase, the tumor assessment does not need to be performed at the EOS Visit if it has been assessed within 8 weeks of the EOS Visit. This does not include a patient who has not been treated by the study drug, such as withdrawal at Screening or at Baseline. Only the electronic Case Report Form (eCRF) required data should be completed. All patients who are withdrawn or removed will not be replaced in this study.

9.3.4 Follow-Up for Drug Discontinuation/Patient Withdrawal from Study

If a patient discontinues study drug and is withdrawn from the study for any reason, the study center must immediately notify the monitor. The date and the reason for study drug discontinuation or patient withdrawal from the study must be recorded on the eCRF. Patients who withdraw from the study are to complete all evaluations for the EOS Visit. If the PI is unable to complete the visit assessments, the reason(s) must be recorded in the eCRF.

10 TREATMENT OF PATIENTS

10.1 Study Drug Treatment and Dosing

Antroquinonol should be taken every 8 hours approximately 15 minutes after a meal or light snack and not within ± 1 hour of drinking an ethanol-containing beverage e.g. an alcoholic drink.

Subjects who forget or are unable to take a dose at the scheduled time should be instructed to take the dose as soon as possible. If they do not remember or are unable to take the dose prior to the next scheduled dose, they should take the scheduled dose and the missed dose will not be made up.

The date and time of each study drug administration should be recorded in the patient diary.

10.2 Treatment for Study Drug Overdose

Treatment of study drug overdose is at the discretion of the investigator.

10.3 Administration on Pharmacokinetic Sampling Days

On the days in Stage 1 when PK sampling will be performed, namely, Days 0 and 28, patients will eat a meal at the study site and then take their next dose of antroquinonol 15 minutes (± 3 minutes) after completion. Patients should take their last dose of antroquinonol on Day 27, approximately 8 hours before the scheduled time of dosing at the study site.

Study drug should be taken at 8-hour intervals, approximately 15 minutes after a meal or light snack, and not within ± 1 hour of drinking an ethanol-containing beverage, e.g. an alcoholic drink. The exact time of study drug administration should be recorded in the patient diary. All capsules must be swallowed within 2 to 3 minutes. On Days 0 and 28 patients will remain at the site for 8 hours after study drug administration if required for PK.

On days of PK sampling in Stage 2, namely, Days 28, 42, and 56, patients will eat a meal at the study site and then take their next dose of antroquinonol 15 minutes (± 3 minutes) after completion. Patients should take their last dose of antroquinonol on Days 27, 41, and 55 approximately 8 hours before the scheduled time of dosing at the study site.

10.4 Extension Phase

After the first 12-week treatment cycle, patients who are progression-free will be eligible to receive further (12-week) treatment cycles with antroquinonol in the Extension Phase.

Patients participating in the Extension Phase will follow a schedule similar to that of the first 12-week treatment cycle, except no PK samples will be drawn. Patients will attend visits every 4 weeks (± 7 days) during the second, third, and fourth treatment cycles. After completion of the fourth treatment cycle, patients will attend visits every 12 weeks (± 7 days).

Patients may continue in the Extension Phase until documented evidence of disease progression, unacceptable toxicity, non-compliance or withdrawal of consent by the patient, or the investigator decides to discontinue treatment, whichever comes first.

If there is Grade 3 or 4 toxicity, the patient's dose will drop down to the next lower dose according to the Dose Modification and Toxicity Management Guidelines in [Section 10.5](#).

10.5 Dose Modification

The guidelines for dose modification and management of drug toxicity are as follows:

Table 10.1 Dose Modification and Management of Drug Toxicity Guidelines

Event	Grade	Management/Action
All non-hematologic and hematologic adverse events that are study drug-related	1 or 2	No change.
	3	Suspend treatment. Treatment may resume if toxicity is resolved to grade ≤ 1 or returns to baseline within 7 days. Treatment should resume at a reduced dose (100 mg t.i.d). If toxicity lasts more than 7 days, study drug will be permanently discontinued (subject to investigator and Medical Monitor agreement); if a patient experiences another grade ≥ 3 toxicity at the reduced dose, then study drug will be permanently discontinued.
	4	

Treatment may be withheld for up to 7 days due to study drug-related toxicities. Patients will be permanently discontinued from the study drug if treatment interruption is more than 7 days and the investigator and Medical Monitor consider that permanent cessation of study drug is necessary. If a patient resumes treatment before the end of a cycle, the patient will have to complete the rest of the treatment of that cycle.

When patients are suspected to experience Grade 3 or more AEs, they should contact the site as soon as possible for an appointment and bring back any unused study drug to the site. Treatment should only be withheld for nausea, vomiting, and diarrhea of Grade ≥ 3 if symptoms remain at Grade ≥ 3 despite adequate treatment. If dose modification is deemed necessary, the unused study drug will be retrieved and a new bottle with quantity of study drugs calculated based on the modified dose will be dispensed. Sufficient study drug should be dispensed for the period from the day of dose modification to the next dispensing visit.

The quantity given will be recorded in the eCRF and the drug accountability log. At the time the patient returns the unused study drug, they will be counted at the site and recorded in the eCRF. The dates and durations of any dosing interruptions will be recorded in the eCRF.

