Two 7-day toxicity studies^{22,23} were performed in both Sprague-Dawley rats and beagle dogs and the maximum tolerated doses (MTD) determined were between 100 mg/kg/day for rats and 100 mg/kg/day for dogs. Two 28-days toxicity studies were conducted to determine no observed adverse effect level (NOAEL) for Sprague-Dawley rats and beagle dogs. The rat NOAEL was 30 mg/kg/day and the high dose of 100 mg/kg/day was not severely toxic.

A NOAEL in the dog was not identified (i.e., loose feces, liquid feces, and vomiting were observed at all doses); the 30 mg/kg/day dose level was tolerated and is the highest non-severely toxic dose (HNSTD).

Toxicokinetic evaluations were performed on a 7-day dog study (100, 250, 500 mg/kg/day single dose, 500 mg/kg/day 3 days dose) and the two 28-day studies mentioned above (Rat: 10, 30, 100 mg/kg/day single and 28 days dose; Dog: 10, 30, 100 mg/kg/day single and 28 days dose). Fast absorption of antroquinonol was repeatedly seen in rats and dogs with peak time (T_{max}) ranging from 0.25 to 6 hours. A trend of dose proportionality in the rat and dog was more or less shown after 1 day of treatment. After 28 days of treatment, rat and dog studies showed inconsistent phenomena in dose proportionality view, one was greater and the other was less than linear in the dose-exposure relationship.

No genotoxicity and no reproductive toxicity (up to 80 mg/kg/day) of antroquinonol was observed via Ames test, mammalian cell gene mutation test, micronucleus test, erythrocyte micronucleus test and *in vivo* study in Sprague-Dawley rats.

As known to the sponsor, no fatal or severe/serious adverse drug reaction has been reported for the marketed product (food supplement) of *Antrodia camphorata*.

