Safety results indicated that antroquinonol at 50, 100, 200, 300, 450, and 600 mg dose levels, given daily for 4 weeks, was generally safe and well tolerated. Antroquinonol at 50, 100, 200, 300, 450, and 600 mg dose levels exhibited a low toxicity profile. Overall, four patients reported four serious adverse events (SAEs) with two patients each in the 450 and 600 mg dose groups. Of these, one patient from each dose group died due to progressive disease and discontinued from the study (one patient in the 600 mg dose group discontinued due to the adverse event [AE] of pleural effusion). None of the deaths, SAEs, and AEs leading to discontinuations was related to the study drug. No Grade 4 treatment-emergent adverse events (TEAEs) were reported as determined by the National Cancer Institute-Common Terminology Criteria for Adverse Events (NCI-CTCAE), Version 4.03.²⁴

Treatment-emergent AEs of toxicity Grade 3 were reported in two patients (one patient in the 200 mg dose group experienced vertigo and one patient in the 450 mg dose group experienced decreased appetite and encephalitis); all events were unrelated to the study drug.

All 13 (100%) patients treated reported TEAEs that were considered treatment-related. The most commonly occurring TEAEs, reported in > two patients, overall, were in the system organ classes of gastrointestinal disorders (12 patients, 92.3% [seven patients in Grade 1, 53.8%, and five patients in Grade 2, 38.5%]), and by preferred term were diarrhea (10 patients, 76.9% [nine patients in Grade 1, 69.2%, and one patient in Grade 2, 7.7%]), vomiting (nine patients, 69.2% [six patients in Grade 1, 46.2%, and three patients in Grade 2, 23.1%]), and nausea (seven patients, 53.8% [six patients in Grade 1, 46.2%, and one patient in Grade 2, 7.7%]).

No patient had any laboratory abnormality recorded as a TEAE except for one case of hematuria of Grade 1 in the 450 mg dose group. Per the sonogram report of the kidney, stones sized 0.47 cm and 0.50 cm in the left kidney without hydronephrosis were noted. The event was considered to be unrelated to the study drug. There were slight increases or decreases in the hematology and biochemistry parameters but none were considered abnormal results.

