13.10.4 Recording AEs and SAEs

All AEs and SAEs should be documented in the source documents and the relevant eCRF and SAE form when applicable. The investigator may be asked to provide photocopies of the medical records for completing the AE or SAE report. The medical records submitted to the relevant parties will be concealed of the patients' names. It is the responsibility of the investigator to report AEs or SAEs by diagnosis terminologies, if possible. When the diagnosis is possible for the reported AE or SAE, no signs and symptoms used to establish that particular diagnosis should be reported. The investigator will be asked to determine the severity and causality of each AE and SAE based on the investigator's clinical judgment. Five levels of intensity and two levels of causality are used to evaluate each AE and SAE as shown below:

Severity based on the National Cancer Institute (NCI) CTCAE version 4.03:

- Grade 1: Mild; asymptomatic or mild symptoms; clinical or diagnostic observations only; intervention not indicated.
- Grade 2: Moderate; minimal, local or non-invasive intervention indicated; limiting age-appropriate instrumental activities of daily living.
- Grade 3: Severe or medically significant but not immediately life-threatening; hospitalization or prolongation of hospitalization indicated; disabling; limiting self-care activities of daily living.
- Grade 4: Life-threatening consequences; urgent intervention indicated.
- Grade 5: Death related to AE.

*There is no direct relationship for severity and seriousness of an AE.

Causality:

- Possibly related: The suspected AE may follow a reasonable temporal sequence from test drug administration but could have been produced or mimicked by the patient's clinical state or by other modes of therapy concomitantly administered to the patient.
- Unrelated: Should be reserved for those events which occur prior to unrelated test drug administration (i.e., washout or single-masked placebo) or those events which cannot be even remotely related to study participation (e.g., injuries sustained in an automobile accident).

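### Section 10.5's exception for nausea, vomiting and diarrhea has no upper grade limit, so it also lifts the mandatory suspension for drug-related Grade 4 vomiting or diarrhea that responds to treatment

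*Protocol*

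**What the plan says.** Table 10.1 (Section 10.5) covers every study drug-related event, hematologic or not. Grades 1 and 2 need no change. From Grade 3, treatment is suspended. The condition for restarting is: "Treatment may resume if toxicity is resolved to grade ≤ 1 or returns to baseline within 7 days". The restart is at 100 mg t.i.d., half the starting dose. If the toxicity lasts beyond 7 days, the drug is stopped permanently, subject to agreement between the investigator and the Medical Monitor.

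The text below the table carves out three symptoms: "Treatment should only be withheld for nausea, vomiting, and diarrhea of Grade ≥ 3 if symptoms remain at Grade ≥ 3 despite adequate treatment".

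Section 13.10.4 gives the severity scale: "Grade 4: Life-threatening consequences; urgent intervention indicated".

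Section 10.4 says that in the Extension Phase a Grade 3 or 4 toxicity moves the patient to the next lower dose, by reference to the Section 10.5 guidelines. Section 9.3.3 allows withdrawal for unacceptable toxicity, or for adverse effects that the investigator thinks require permanent cessation.

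**The concern.** An exception for manageable Grade 3 nausea, vomiting or diarrhea is a reasonable choice for an oral drug whose main known toxicity is gastrointestinal. This one does not stop at Grade 3. It reaches events that the protocol itself calls life-threatening, and no reason is given for including them.

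The excepted symptoms are the ones most likely to occur. Section 7.4 reports diarrhea in 10 of 13 Phase 1 patients, vomiting in 9 and nausea in 7. Section 7.3 reports that no NOAEL was identified in dogs because "loose feces, liquid feces, and vomiting were observed at all doses". What is at stake is a mandatory safety step: a pause and a halved dose, required for other drug-related Grade 4 events but not for a Grade 4 event of this type that responds to treatment.

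**Working it through.** The plan gives no figure to reproduce, so the check is a reading of the rules side by side.

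**Assumption on the table.** In the available text the Grade 4 action cell is empty. I read it as sharing the Grade 3 action, because Section 10.4 also groups Grades 3 and 4.

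**Required action for a drug-related Grade 4 event in the first 12-week cycle**

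| Step | Any other event (Table 10.1) | Vomiting or diarrhea (exception) |
|---|---|---|
| At onset | Suspend | No suspension required while treatment is tried |
| Symptoms stay at Grade 3 or above despite treatment | Remains suspended | Withhold; Table 10.1 then applies |
| Symptoms fall below Grade 3 on treatment | Resume only at Grade 1 or less, or baseline, within 7 days | No suspension required, even if symptoms settle at Grade 2 |
| Dose afterwards | 100 mg t.i.d. | No reduction required |

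The last row is an inference. The only specified route to 100 mg t.i.d. in Section 10.5 is resumption after a suspension, so an event that is never withheld does not trigger it.

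**Dose consequence.** Starting dose: 3 × 200 mg = 600 mg/day. Reduced dose: 3 × 100 mg = 300 mg/day. For a responding Grade 4 event, Table 10.1 alone would require 0 mg until recovery and then 300 mg/day. Under the exception, no change from 600 mg/day is required.

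**How often.** Section 7.4 states: "No Grade 4 treatment-emergent adverse events (TEAEs) were reported". Nausea, vomiting and diarrhea there did not exceed Grade 2. The protocol gives no expected Grade 4 rate, so the rates *r* below are assumptions. The formulas are: no case in 13 patients, (1 − r)^13; at least one case in 60, 1 − (1 − r)^60; expected cases in 60, 60r.

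| Assumed r | No case in 13 | At least one in 60 | Expected in 60 |
|---|---|---|---|
| 0.5% | 0.995^13 = 94% | 1 − 0.995^60 = 26% | 0.3 |
| 1% | 0.99^13 = 88% | 1 − 0.99^60 = 45% | 0.6 |
| 2% | 0.98^13 = 77% | 1 − 0.98^60 = 70% | 1.2 |

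A clean Phase 1 record in 13 patients is therefore compatible with a case or two in this trial. These are counts of all Grade 4 events of this type. The gap concerns only those that respond to treatment, which are fewer.

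**The case against.** A reader might infer that the protocol compels full dosing through a life-threatening event, or forbids any pause or reduction. The documents do not support that.

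- The sentence after the exception provides for dose modification where it is deemed necessary, and does not make a prior suspension a condition.
- Section 10.5 also permits withholding for up to 7 days for drug-related toxicity, with no grade stated. The exception narrows this for the three symptoms, but the section is headed as guidelines and the sentence says *should*.
- Patients who suspect a Grade 3 or worse event are told to contact the site promptly and bring back unused drug. That is not a stop order, but it brings the decision to the site.
- Section 10.1 allows for doses that a patient is unable to take, so uninterrupted dosing during life-threatening vomiting is unlikely in practice.
- Section 9.3.3 allows withdrawal, and Section 15.2 allows departure from the protocol in medical urgency.
- In the Extension Phase, Section 10.4 calls for a dose drop at Grade 3 or 4. It does so by reference to Section 10.5, so it either defers to the exception or conflicts with it.

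A second tempting reading is that the protocol has no pause-and-reduce step for any severe gastrointestinal toxicity. It does: events that persist at Grade 3 or above despite treatment are still withheld.

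Two pieces of background deserve little weight. The criterion barring "Grade > 2 diarrhea of any etiology at baseline" governs entry and does not speak to on-treatment management. Section 7.3 also says the 30 mg/kg/day dose was tolerated in dogs.

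All of this limits the consequence without removing the gap. Each route in the first cycle is discretionary, a permanent stop, or a departure from the protocol. None restores a required hold at Grade 4.

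**Conclusion.** The point holds in a limited form. As written, the exception removes the mandatory immediate suspension, and the half-dose restart that follows it, for drug-related Grade 4 vomiting or diarrhea that responds to treatment. In the first 12-week cycle a pause or reduction is then left to judgement. In the Extension Phase the protocol is unclear, because Sections 10.4 and 10.5 pull in different directions.

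The conclusion rests on a literal reading of the grade range and on Grade 4 sharing the Grade 3 action in Table 10.1. The number of patients affected is probably very small: 0.3 to 1.2 Grade 4 cases among 60 at assumed rates of 0.5% to 2%, before counting only responders. The primary endpoint, decision thresholds and sample size are untouched. It is worth correcting because the protocol defines the events as life-threatening, does not explain their inclusion, and could close the gap with little effort.

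**What to change.** Limit the exception to Grade 3 and state the Grade 4 rule outright, for example: *For Grade 3 nausea, vomiting or diarrhea, withhold treatment only when symptoms persist at Grade 3 or above despite adequate treatment. For any drug-related Grade 4 event, vomiting and diarrhea included, suspend treatment at once and follow Table 10.1.* This also removes the tension with Section 10.4 for Grade 4 events.

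The cost is two sentences in Section 10.5. Because the change bears on patient safety, it would be a substantial amendment under Section 18.1, with notice to sites. The few patients with a controlled Grade 4 event would lose up to 7 days of dosing and resume at 300 mg/day, or stop if they had not recovered. No patients, visits or procedures are added.
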